4.3 Study Enrollment Procedures

Identifying survey participants

The PI has already established a strong network with the Bhutanese community and completed her needs assessment studies collecting determinants of a mental health problem through engaging community members in the research process. We will use an existing community network to spread the study information in coordination with church leaders, community research assistants (RAs), and supervisors. PI will prepare an oral script including study objectives, eligibility criteria, intervention procedure, study and survey information, hair sample collection, and informed consent procedure. It will also distribute it to them to spread the study information. They will be requested to disseminate the information about the study purpose and process to their community in phone or in-person meetings in any of their gatherings, word of mouth, formal/informal discussions, and festivals to check-in for their interest to participate in the study. Interested participants will be requested to contact PI, RAs, and supervisors.

Recruiting survey participants

Community RAs from the local area will be mobilized to reach interested families to check their eligibility and make a list of eligible participants. Eligibility criteria for participants are: being Bhutanese adults 18 years or older resettled in Massachusetts with a score of 14 or below on the Patient Health Questionnaire-9, showing commitment to complete the intervention procedure, and giving informed consent to participate in the study. RAs will recruit interested eligible participants with their informed consent and will conduct a baseline survey. RAs will be asked to leave a note in the screening tool and screening log of reasons for ineligibility, such as a PHQ-9 score of more than 14 or any history of clinically diagnosed mental health problems or taking any medication related to mental health problems. RAs will also leave a note for non-participation of eligible candidates in the screening tool and screening log.

Randomizing study participants for intervention and control

We will randomly allocate selected families into intervention and control groups using a random sampling method after the baseline survey. We will randomly assign 116 interested

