families (58 families per intervention and control) using a random number table. For random allocation, first, PI will prepare the sampling frame that lists interested families. Second, assign a number to each family in the sampling frame. Third, select 116 numbers using a table of random numbers. PI will request any interested community member to point one number in the random number table by closing his/her eyes. Since the selected families total 116, or three digits, we will choose only the first three digits of the number chosen as the first sampled family. Finally, we will choose other numbers moving down the first number column until all 116 families will be selected.

We will assign a random number selected at the first attempt for intervention and the second attempt for control. It means random numbers selected at odd attempts (first, third, seventh,) will be assigned for intervention and at even attempts (second, fourth, sixth...) for control. The sample elements corresponding to the selected random numbers become the sample. Procedures are in place for tracking the participants for intervention and follow-up (e.g., contact address and phone). RAs will visit selected families and brief them about study procedures, informed consent, and procedures to protect human subjects. All adult members of selected families who meet the inclusion criteria and give informed consent will be recruited for the study. We will follow up with all families randomized to either study arm. We will not follow up with participants if they decide to end their participation at a particular time point of our study. But, we will include their already collected data in our analysis. Given our strong community networks and mobilization of community RAs, we anticipate low attrition rates in practice. Ethical approval for our study will be obtained from the Institutional Review Board at UMass Amherst.

Recruitment of focus group discussion participants

PI will collect data on engagement, acceptability, and satisfaction of intervention delivery by conducting focus group discussions (FGD) with selected interested participants who are already enrolled in our study from the intervention group (30) upon intervention completion using a brief guide questionnaire. The participant will be eligible to attend the focus group discussion if they are already enrolled in our intervention group and have attended our mental health promotion program. RAs will inform participants about FGD

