9 STATISTICAL CONSIDERATIONS

9.1 Sample Size and Randomization

The pilot project aims to estimate the magnitude of the difference between the preventive intervention and the education control on the primary outcomes of interest (stress, anxiety, depressive symptoms) to inform the design of a large-scale intervention. A study comparing PMP to a treatment-as-usual control in Pakistan⁶¹ found a mean difference of about 7 points with a standard deviation of 8.5 on a measure of anxiety and depression for effect size ($ES=.86$). We do not expect our ES to be as large as what was observed in the Pakistani study⁶¹ given that we are doing a prevention trial and not an intervention study in a distressed population so that this study will provide an estimate of the ES of PMP as a preventive intervention.

We conducted a power analysis to detect an ES as small as $ES=.30$ with $\alpha = .05$ and power of $.80$. We may find a larger effect in our pilot, but our understanding is that power estimates should be based on the smallest effect that we want to detect rather than the size of the effect that we expect.⁶² We expect that families will average approximately 2-4 adult persons based on our pilot data, and conducted our power analysis to account for the correlation among family members. Analyses were conducted using Optimal Design,⁶³ which is power analysis software created for cluster randomized trials such as the present study. Accounting for the intra-correlation among family members of $.10$ and $\alpha = .05$, we would have 80% power to detect a standardized difference of $ES=.30$ between two treatment groups of 116 families (58 per treatment arm) with an equal probability of being randomized to each of our two intervention arms.

As noted above, we do not expect our ES to be as large as in the Pakistani study, but a sample of that size should be sufficient to provide the estimates of the differences between the conditions (with standard deviation in our sample) and the correlations between the targets specified by theory and our primary outcome of interest to inform the design of a larger-scale controlled trial. The other goal for the project is to determine whether the intervention affects the target mechanisms specified by theory to mediate or moderate the intervention's impact on the outcomes. Those estimates we will get from the correlation between our respective targets (coping and self-efficacy) and the primary outcomes.

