content analysis.⁵³ Feedback provided by the field staff will be reviewed and coded to identify recurrent themes regarding the intervention's acceptability. All analyses will be conducted in the Nepali and translated into English. Fidelity data will be used to assess intervention content and transmission. We will determine retention by obtaining proportions of participants attending all or portion of sessions.

Aim 2b Intervention efficacy: We will carry out data management and descriptive analyses for study outcomes. Means, standard deviations, and percentile distributions will be used to describe the continuous baseline variables. Frequencies and percentages will be used to describe categorical variables. We will compare baseline characteristics of intervention and control groups using chi-square and t-tests as appropriate. While differences between groups are not expected because of the randomization used in the study design, variables showing significant differences between the two groups will be included as covariates in primary analyses. We will compare participants' characteristics to follow-up to those with complete data to assess potential limitations in recruitment and retention.

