The primary analyses will test whether participants' outcomes in the PMP-I arm differ from those in the control arm. Multilevel modeling will compare outcomes of each treatment arm while accounting for the clustering of participants within families. Continuous outcomes will be analyzed using hierarchical linear modeling, and dichotomous outcomes will be analyzed using multilevel generalized linear models with a Bernoulli distribution appropriate to nonlinear binary outcomes.⁶⁴ We expect approximately 2-4 members for each of the 58 families in each treatment arm, and the correlation among family members' responses will be accounted for in the model. Hierarchical or multilevel modeling is suited to these data as it accounts for the clustering of members within families and unbalanced designs (i.e., different family sizes).⁶⁴ This will be an intention-to-treat type of analysis, as multilevel modeling allows retention of all participants irrespective of the number of sessions attended (multilevel modeling uses maximum likelihood estimation, one of the recommended ways of handling missing data). The analysis will estimate endpoint outcomes based on repeated measures (Level 1) within individuals (Level 2) within families (Level 3). This three-level model is represented by the following equations:

Level 1: $Outcome_{ijk} = \pi_{0jk} + \pi_{1jk} * Time_{ijk} + e_{ijk}$; Level 2: $\pi_{0jk} = \beta_{00k} + r_{0jk}$; $\pi_{1jk} = \beta_{10k} + r_{1jk}$
 Level 3: $\beta_{00k} = \gamma_{000} + \gamma_{001} * PMP-I_k + u_{00k}$; $\beta_{10k} = \gamma_{100} + \gamma_{101} * PMP-I_k + u_{10k}$

[figure not shown]

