Figure 1 provides a visual representation of our proposed analyses, in which treatment is a predictor of treatment targets or mechanisms (i.e. the mediators such as coping), which are in turn associated with outcomes. As reviewers 1 and 3 note, in mediational analyses, variables must be measured in *temporal sequence*.

Figure 2 provides a visual representation of our proposed temporal sequence of variable measurement for mediational analyses, in which treatment randomization occurs before mediator target measurement, which in turn are collected before the outcome measure used in the proposed analyses. Second, it is crucial to test the *indirect effect* (a*b paths) of the treatment on the outcome through the hypothesized mediators. As the indirect

effect is not normally distributed, we will assess its significance via Monte Carlo simulated confidence intervals, which are the recommended counterpart in multilevel mediation to bootstrapped confidence intervals used in single-level analyses.⁶⁶⁻⁶⁸

Each potential mediational sequence will be tested in this manner (see **Table 1** for mediators and outcomes to be tested). While we acknowledge that mediational analyses are difficult to adequately power in a sample of our proposed size,⁶⁷ we believe these preliminary analyses will help identify potential mechanisms for our treatment effect. If baseline differences in treatment groups are found in either the mediating or outcome variables, baseline measures will be controlled for in all analyses. Sample mixed-format multilevel equations are provided below, where the nesting of measures (i) within families (j) is accounted for by the random effects u_{0js} : γ_{01} in the Mediator equation is the ‘a path’, and γ_{10} in the Outcome equation is the ‘b path.’

Table 1 Mediators and Outcome Variables

Mediators (Targets)	Outcomes
Coping, Self-Efficacy	Perceived Stress
Family or Social Support	Physiological Stress
Family Conflict Resolution	Anxiety Symptoms
Family Satisfaction	Depressive Symptoms
Family or Social Network	

$$T2Mediator_{ij} = \gamma_{00_Med} + \gamma_{01_Med} * TreatmentCondition_j + u_{0j_Med} + r_{ij_Med}$$

$$T3Outcome_{ij} = \gamma_{00_Out} + \gamma_{10_Out} * T2Mediator_{ij} + \gamma_{01_Out} * TreatmentCondition_j + u_{0j_Out} + r_{ij_Out}$$

The key estimates are the association of the treatment condition with the mediator (γ_{01_Med} , a path) and the association of the T2 mediator with the T3 Outcome (γ_{10_Out} , b path).

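### Baseline chi-square and t-tests ignore family clustering, so their p-values, and the covariate rule that depends on them, do not hold the nominal 5% level

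*Combined protocol and SAP*

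**What the plan says.** Section 4.3 makes the family the unit of allocation: "We will randomly allocate selected families into intervention and control groups using a random sampling method after the baseline survey". The people analysed are individual adults: "All adult members of selected families who meet the inclusion criteria and give informed consent will be recruited for the study". Section 9.1 treats the study as a cluster randomised trial with 116 families, 58 per arm, and a within-family correlation of .10. On family size it says: "We expect that families will average approximately 2-4 adult persons based on our pilot data". Section 9.2 chooses multilevel modelling for the outcomes partly because "it accounts for the clustering of members within families and unbalanced designs".

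The baseline comparison under Aim 2b is the exception: "We will compare baseline characteristics of intervention and control groups using chi-square and t-tests as appropriate". The result has a consequence: "variables showing significant differences between the two groups will be included as covariates in primary analyses".

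Aim 2c has a second rule: "If baseline differences in treatment groups are found in either the mediating or outcome variables, baseline measures will be controlled for in all analyses". That sentence names neither a test nor a criterion for a difference. The planned comparison of participants by completeness of follow-up also names no test.

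**The concern.** An ordinary t-test or chi-square test takes each adult as an independent observation. Here all adults of a family are in the same arm, and the plan expects their answers to be correlated. With positive correlation the variance of the difference between arms is larger than the test assumes, so chance differences are called significant more often than 5% of the time. Nothing in the documents moves these tests to family level or adjusts them for clustering, and the qualifier at the end of the sentence reads most naturally as choosing the test by type of variable.

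Two things are at stake. The baseline table may report imbalance between properly randomised arms on the strength of wrong p-values. And the Aim 2b rule lets those p-values decide which covariates enter the primary model.

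**Working it through.** **Inputs.** 116 families, 58 per arm, correlation .10, alpha .05 (two-sided assumed) and effect size .30, all from 9.1. Adults per family m: 2 to 4 from 9.1, or 226/116 = 1.95 from the 226 adults stated in the synopsis.

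**The plan's own figure.** The documents give no error rate for the baseline tests. The related figure is the 80% power in 9.1. The noncentrality is 0.30/√[4(0.10 + 0.90/m)/116], with 114 degrees of freedom. At m = 4 this is 0.30/√(4 × 0.325/116) = 2.83, and power is 80.2%. At m = 3 power is 71.7%, and at m = 2 it is 57.9%. So the stated power reproduces at the top of the family-size range only. The conflict with 226 adults is a separate point; here it means both ends of the range must be shown.

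**True size of the unadjusted test.** The design effect is DEFF = 1 + (m − 1) × ICC. The true size is 2 × [1 − Φ(1.96/√DEFF)].

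| Adults per family | DEFF at ICC .10 | 1.96/√DEFF | True size |
|---|---|---|---|
| 1.95 | 1.095 | 1.873 | 6.1% |
| 2 | 1.10 | 1.869 | 6.2% |
| 3 | 1.20 | 1.789 | 7.4% |
| 4 | 1.30 | 1.719 | 8.6% |

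Simulating 116 families (8,000 runs per setting) gave 5.9%, 7.5% and 8.0% for m = 2, 3 and 4, and 7.3% for mixed sizes of 2 to 4. A t-test on family means in the same runs gave 4.7% to 5.3%.

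**Other correlations (assumed; the documents give only .10).**
- ICC .30: 8.4% at m = 1.95 to 15.5% at m = 4.
- ICC .50: 10.6% at m = 1.95 to 21.5% at m = 4.
- ICC −.10 at m = 2: DEFF = 0.90, 1.96/√0.90 = 2.066, size 3.9%.

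The family conflict resolution and family satisfaction scales ask several adults about the same family, so they may well exceed .10. Sex within couples is likely to be negatively correlated.

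**Effect on the primary test.** A null simulation used 116 families of three, one baseline covariate, and regression on family means as a stand-in for the multilevel model (4,000 runs per setting). The covariate's ICC was .10 or 1 and its correlation with the outcome .3 or .6, all assumed. When the unadjusted test decided on adjustment, the type I error of the treatment test was 2.0% to 5.0%. When a family-level test decided, it was 3.2% to 5.1%. The standard deviation of the estimate was slightly smaller with the unadjusted trigger in all four settings: .116 v .117, .108 v .110, .116 v .121 and .111 v .134.

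**The case against.** The strongest reply is that little follows for the trial's conclusions. The treatment test is multilevel whatever the baseline tests show. A false flag only adds a covariate measured before randomisation, which does not bias the effect estimate and, in the simulation, slightly sharpened it. A reader might infer that the primary type I error is inflated; the documents and the calculation do not support that. This part of the reply stands.

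A reader might also reach for much larger error rates. A characteristic shared by the whole household (ICC 1) would give 16.6% to 32.7% for two to four adults per family. A mix of ten independent variables, three of them fully shared, would give a 63% to 84% chance of at least one false flag. But the visit schedule lists only demographics, without saying which, and no such correlation appears anywhere. If all ten had ICC .10, the chance would be 47% to 59% for two to four adults, against 40% for ten valid tests. Most of that is multiple testing, not clustering.

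Nor can one say that every baseline standard error is too small, since negative correlation reverses the direction. And the Aim 2c rule and the retention comparison cannot be called wrong as written, because they name no test.

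Finally, selecting covariates by significance is the deeper weakness: a valid test would still flag about 5% of variables by chance. That is true, and it shapes the fix. It does not make the tests valid.

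**Conclusion.** The point holds in limited form. At the plan's own correlation, a nominal 5% baseline test runs at about 6.1% to 8.6%, depending on whether families average 1.95 or 4 adults. Larger or smaller departures depend on correlations that the documents do not give. The calculation assumes two-sided tests on individual adults and roughly equal family sizes; mixed sizes changed little.

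The consequence is misreported imbalance and a primary covariate set chosen by p-values that do not mean what they state. Only the Aim 2b rule is explicitly tied to these tests. The Aim 2c rule and the retention comparison share the fault only if they are carried out the same way, though the Aim 2b tests are the only baseline comparison of arms that the plan describes. There is no evidence of damage to the primary test. The correction is still worth making, because the baseline sentence contradicts the design that the same section is built on, and it costs almost nothing.

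**What to change.** In 9.2, Aim 2b, present baseline characteristics by arm as means, percentages and standardised differences without p-values. If tests are kept, use a mixed model or GEE with a family effect.

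In the same place, replace the significance rule with covariates named in advance: at least the baseline value of each outcome and mediator, which 6.2.2 already collects. Without this step, dropping the tests would leave the rule with no criterion, and correcting them would give up the small gain in precision seen above. State whether the baseline value enters the three-level model as a covariate or as a Level 1 measurement. It should not be both, and if it leaves Level 1, only two time points remain and the individual random slope would have to go.

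Use the same named covariates in Aim 2c in place of its conditional sentence, and a family-clustered method for comparing followed and lost participants.

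The cost is a few sentences in 9.2 and a little more code, with no new data. There will be fewer nominally significant baseline differences to report.

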Where the outcome is measured at each repeated measure *i* for each individual *j* within each family *k*. Time is centered at the endpoint, so that β_{00k} estimates the value of the outcome for each family at the end of the study, informed by all data points available for that family. If an endpoint observation is missing due to drop out, the advantage of multilevel modeling is that it utilizes maximum likelihood estimation, which estimates the expected outcome for that cluster using information from prior assessments as well as the expected value from the entire model. The key test of difference in the outcome between the treatment groups is represented by γ_{001} (in bold); this is a test of difference in outcome at endpoint between families randomized to PMP versus not. We expect this test of difference to be statistically significant based on our power analysis for the difference in outcome *level* at the endpoint. Note that this model will also test group differences in *change* in each outcome (γ_{101}). While our pilot is not powered for the significance of effects of change over time, we will be able to obtain estimates of ES for change for use in future larger-scale trials and analyses.

The ultimate goal of our analyses is to estimate the ES for this prevention trial for each outcome, to inform our planning of a full-scale trial. As noted earlier, we have powered this pilot prevention trial with a conservative estimate of effect size based on a similar study in a clinical population, but no known studies have characterized the precise effect size of PMP as a preventive intervention; a goal of our pilot is to estimate the expected effect on the population of interest (i.e. an at-risk vs clinical population). All analyses will be performed using SAS, version 9 (SAS Institute Inc, Cary, NC).

Aim 2c Mediating effects: Separate models will be created to evaluate the relationships between mediators (targets) and outcomes and to explore mediators (e.g. coping) of intervention-outcome relation.

In this aim, we aim to test the potential *mediators* of the treatment-outcome association by conducting mediational analyses in a multilevel regression framework.⁶⁵ Following current

[figure not shown]
Figure 1 Mediational Analysis Framework

recommended best practices in mediational analysis, we will conduct these analyses using recommended practices for mediation with a multilevel framework.⁶⁶⁻⁶⁸

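### Baseline scores should always enter the Aim 2b and Aim 2c models, not only when the arms happen to differ

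*Combined protocol and SAP*

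**What the plan says.** **Aim 2b (section 9.2).** Arms are compared at baseline with chi-square and t-tests, and "variables showing significant differences between the two groups will be included as covariates in primary analyses". No baseline score is named in advance as a covariate. The primary model has three levels: repeated measures within persons within families. Baseline, post-intervention and 3-month scores are all Level 1 responses, and time is centred at the endpoint. Arm has its own effect on the endpoint level (γ001) and on the slope (γ101). "The key test of difference in the outcome between the treatment groups is represented by" γ001.

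**Aim 2c (section 9.2).** "If baseline differences in treatment groups are found in either the mediating or outcome variables, baseline measures will be controlled for in all analyses". The sample equation for the T3 outcome holds only the T2 mediator, treatment and a family effect.

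**Purpose.** Section 9.2 states: "The ultimate goal of our analyses is to estimate the ES for this prevention trial for each outcome". Section 9.1 adds that the sample should provide "the correlations between the targets specified by theory and our primary outcome of interest to inform the design of a larger-scale controlled trial".

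**The concern.** After randomisation, any arm difference at baseline is chance. A baseline covariate is worth including because it predicts the outcome, whatever its chance imbalance. A significance screen therefore selects on the wrong property and usually leaves the best predictor of the endpoint, its own baseline score, out of the covariates.

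In Aim 2c the same kind of trigger fails for a different reason. Treatment is randomised, so balance is relevant to the treatment-to-mediator path (a). The mediator is not randomised. People who cope better at baseline may also have lower stress at 3 months within each arm, however well the arms balance. That association passes into the mediator-to-outcome path (b) and from there into the indirect effect.

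This pilot is meant to deliver effect sizes and candidate mechanisms for a larger trial. The first would be less precise than the collected data allow, and the second could point to the wrong target.

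**Working it through.** **Inputs.** From section 9.1: effect size .30, α = .05 (taken as two-sided), intra-family correlation .10, 116 families in two equal arms, about 2–4 adults per family. The synopsis gives 226 adults, which is 226/116 = 1.95 per family. Not in the documents and therefore assumed: baseline-endpoint correlation r = .3, .5 or .7 (the same within and between families), complete data, and the mediation settings in step 4.

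**1. The plan's own figure.** Per-family variance v = .10 + .90/n, noncentrality λ = ES²/(4v/116), F test on 1 and 114 df. For n = 4, v = .325, λ = .09/(1.3/116) = 8.03, power .802. This reproduces 80%. For n = 3 power is .717; for n = 1.95 it is .570. The dependence on family size is a separate matter.

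**2. How often the screen fires.** A t-test that ignores families rejects by chance with probability 2[1 − Φ(1.96/√(1 + (n − 1)·.10))] = .062, .074 and .086 for n = 2, 3 and 4. A given baseline score is adjusted for in only about 6–9% of trials.

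**3. What the planned growth model recovers.** With days 0, 42 and 132 and equal correlations, the generalised least squares weights on the three arm differences are −.139, .203 and .935. Baseline gets weight −.139 whatever r is; adjusting the endpoint for baseline gives it −r. Variance relative to the raw endpoint, over time coded 0/42/132 or 0/1/2 and over equal or decaying correlations:

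| r | planned model | baseline always used (1 − r²) |
|---|---|---|
| .3 | .88–1.00 | .91 |
| .5 | .92–1.00 | .75 |
| .7 | .95–1.00 | .51 |

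Putting v × factor into the formula of step 1 gives power for ES .30 (planned vs baseline always used):

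| adults per family | r = .3 | r = .5 | r = .7 |
|---|---|---|---|
| 4 | .80–.85 vs .84 | .80–.84 vs .90 | .80–.82 vs .98 |
| 3 | .72–.77 vs .76 | .72–.75 vs .83 | .72–.74 vs .94 |
| 1.95 | .57–.62 vs .61 | .57–.61 vs .69 | .57–.59 vs .85 |

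For n = 4 the 95% half-width for the effect size is 1.96 × 2√(.325/116) = .207 for the raw endpoint. At r = .5 it is .20–.21 under the planned model and .207 × √.75 = .18 with baseline used.

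**4. The b path.** Suppose the mediator has no true effect (b = 0), and mediator and outcome each depend on their own baseline. Without baseline terms the expected estimate of b is r(M0,Y0) × stability of M × stability of Y. With stability .6 and a baseline correlation of −.3, −.4 or −.5 this is −.3 × .36 = −.11, −.14 or −.18. Simulated false indirect effects (autoregressive model):

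| true a (SD) | Aim 2c rule as written | baseline always included |
|---|---|---|
| .2 | 10–21% | 1–5% |
| .3 | 18–40% | 1–5% |
| .4 | 27–59% | 1–5% |

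The 1–5% is the range over all three rows. At a = 0, leaving out the baseline terms gives only 1–4%. A variant with families of three, a = .3, baseline correlations .3–.7 and stabilities .5 or .7 gives 17–66% under the rule and 4–6% with baseline. There the trigger fired in 12–15% of runs, so b stayed unadjusted in most trials.

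If mediator and outcome are instead stable traits measured with error, false indirect effects at a = .4 are 79–85% without baseline terms and still 24%, 45% and 75% with them.

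**The case against.** **Baseline is already in the primary model.** This is true: it is a Level 1 response and helps when an endpoint is missing. The loss in step 3 comes from leaving the baseline arm means free, so deleting the screen alone would recover almost nothing. Adding baseline as a covariate while keeping it as a response would use it twice. Both points stand, and they decide the form of the fix.

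**Aim 2b is only a matter of efficiency.** Also true. In a simpler simulated endpoint test, type I error under the conditional rule was .029–.052. Every gain depends on an r the documents do not give. At r = .3 with time coded 0/1/2 and equal correlations, the planned model is slightly better than adjustment (.88 vs .91). Restricting the analysis to PHQ-9 scores of 14 or below may also lower r.

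**The mediation figures rest on strong scenarios.** In part. An a of .4 SD exceeds the design effect size of .30, which is why the .2 and .3 rows are shown. In the trait case, if stability .6 is read as reliability, an observed correlation of −.5 implies a latent one of −.5/.6 = −.83, which is extreme.

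**The plan already calls these analyses preliminary.** It does ("we believe these preliminary analyses will help identify potential mechanisms for our treatment effect"), concedes low power, orders the measurements in time and labels its equations as samples. Those caveats concern imprecision and sequence. Neither removes confounding by baseline status.

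**Conclusion.** The concern holds on both counts and should be corrected before analysis.

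For Aim 2b it is a loss of precision, with no bias in the randomised comparison and no error in the stated 80%. It is negligible at r = .3, worth roughly 6 to 10 points of power at 4 per family and r = .5, and larger at r = .7.

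For Aim 2c it is an error of logic whatever correlations are assumed: a check of arm balance cannot address confounding of a path that was not randomised. Its size depends on the assumed stabilities, the baseline mediator-outcome correlation and the true a. It becomes material only if treatment really moves the mediator. Baseline adjustment removes the bias under the autoregressive model but only part of it under the trait model.

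**What to change.** 1. **Aim 2b.** Delete the significance screen. Always use the baseline value of the outcome, in one of two ways: constrain the arm means to be equal at baseline in the repeated-measures model, or take baseline as a covariate with only Day 42 and Day 132 as responses. Name any other covariates in advance.
2. **Aim 2c.** Always put the baseline mediator in the T2 mediator equation, and the baseline mediator and baseline outcome in the T3 outcome equation.
3. **Sensitivity analysis.** Report how strong residual mediator-outcome confounding would have to be to change the result, for example the residual correlation at which the indirect-effect interval would include zero. Label indirect effects as exploratory.

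The cost is revised analysis wording and a few degrees of freedom. Section 6.2.2 already lists the outcome and mediator scales as baseline assessments, so no participants, visits or measurements are added.
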